7.8.2 Subgroup analysis for Study Region (Japan, Korea, Taiwan)

For Study Region (Japan, Korea, Taiwan), following secondary efficacy endpoints, safety endpoints, and pharmacodynamics endpoints will be analyzed in addition to 7.8.1 Subgroup analysis of primary endpoint and treatment emergent adverse events.

- ACR50
- ACR70
- DAS28-CRP
- DAS28-ESR
- Pharmacodynamics endpoints
 - Vascular Endothelial Growth Factor (VEGF)
 - Matrix metalloproteinase 3 (MMP-3)
- Overview of TEAEs
- Serious TEAEs
- Drug related TEAE
- TEAE leading to permanent discontinuation of study drug or reference drug
- The number and percentage of subjects with TEAEs of special interest
 - Serious Infections
 - Malignancies
 - Herpes Zoster Related Disease (Herpes Zoster and Varicella)
- Clinical Laboratory Evaluation
 - For continuous variables, descriptive statistics of raw values, change from baseline value at each scheduled visit will be summarized at each time point using SI unit
 - For categorical variables, frequencies and percentages will be displayed at each scheduled visit.

7.8.3 Protocol Version Number (used for confirmation of the Inclusion criteria and the Exclusion criteria) (\leq Version 2.0, \geq Version 3.0)

For Protocol Version Number (used for confirmation of the Inclusion criteria and the Exclusion criteria) (\leq Version 2.0, \geq Version 3.0), following secondary efficacy endpoints and safety endpoints will be analyzed in addition to 7.8.1 Subgroup analysis of primary endpoint and treatment emergent adverse events.

- ACR50

- ACR70
- DAS28-CRP
- DAS28-ESR
- Serious TEAEs
- The number and percentage of subjects with TEAEs of special interest
 - Serious Infections
 - Malignancies
 - Herpes Zoster Related Disease (Herpes Zoster and Varicella)

7.9 Other Analyses

Not Applicable.

7.10 Interim Analysis (and Early Discontinuation of the Clinical Study)

Not applicable for efficacy analysis. Review of safety data and safety evaluation will be completed by an independent DSMB during the study in accordance with separate SOP.

7.11 Handling of LLOQ, Missing Data, Outliers, Visit Windows, and Other Information

7.11.1 LLOQ

Safety variables

Values below the LLOQ for beta-D-glucan, hCG, Troponin-T, CK-MB will be treated as it is and these variables are not used for descriptive statistics and displayed in the listings. As for beta-D-glucan, it is used for shift-from baseline analysis.

PD variables

Values below the LLOQ will be set to 0 for calculation of descriptive statistics.

7.11.2 Missing Data

Missing Data in ACR20/50/70, DAS28

Table 8 addresses the handling of missing ACR components and ACR response in the inferential analyses of ACR20/50/70, DAS28, and DAS28-related variables at Week12/ET. Note that if subject does not have any post-baseline values, then that subject will be defined as an ACR20-CRP non-responder. Moreover, if subject does not have baseline values, then that subject will be defined as an ACR20-CRP non-responder.

For ACR20/50/70, if some of ACR components include missing, then the following handling will be done.

	TJC-68	SJC-66	Remaining 5 Components	ACR20/50/70
Pattern 1	Non-Responder	Any	Any	Non-Responder
Pattern 2	Any	Non-Responder	Any	Non-Responder
Pattern 3	Any	Any	The Number of the Response is Less than 3 Components.	Non-Responder
Pattern 4	Missing	Responder or Missing	The Number of the Response is at least 3 Components, or the Number of the Missing is at least 3 Components.	Missing
Pattern 5	Responder or Missing	Missing	The Number of the Response is at least 3 Components, or the Number of the Missing is at least 3 Components.	Missing
Pattern 6	Responder or Missing	Responder or Missing	The Number of the Missing is at least 3 Components (Baseline=0 regarded as Non-Responder).	Missing
Pattern 7	Responder	Responder	The Number of the Response is at least 3 Components.	Responder

Table 8. Imputation Methods for Missing ACR and DAS28 for Components and Response at Week 12/ET

Imputation Method		Explanation/Instruction
For use in all ACR20/50/70 analyses at Week 12/ET including primary analysis.		
1	LOCF components	
 • First LOCF all missing ACR component value(s) at Week 12 and then calculate ACR response as Week 12/ET.
For use in sensitivity analysis of ACR20-CRP at Week 12/ET		
2	LOCF components and NRI response	
 • If all ACR component values are missing at Week 12 for any reason and therefore the ACR response is missing, the missing ACR response at Week 12/ET will be imputed using NRI (i.e., subject is a non-responder). • If NOT all ACR component values are missing at Week 12 for any reason, all missing ACR component value(s) at Week 12/ET will first be imputed using LOCF and then the ACR response will be calculated.
3	Observed	
 • Data as observed (i.e., data as reported in the study database) will be analyzed. Missing ACR response components will remain missing if reported in the study database as missing. Missing ACR response will remain missing. 
*: ACR20 at Week 12 is used for this sensitivity analysis

Imputation Method		Explanation/Instruction
4	Multiple Imputation, assuming Missing at Random Mechanism	
Multiple imputation (MI) will be conducted in the following procedure.
 
<Step1>Imputation Part
 
1) Multiple Imputation for Non-Monotone Missing data If non-monotone missing pattern exists, then those non-monotone missing data will be imputed by adapting Markov Chain Monte Carlo method, using each non-missing ACR components data up to Week 12. Imputation will be conducted by each ACR components (i.e. TJC-68, SJC-66, SGAP, SGA, PGA, HAQ-DI, CRP), and treatment groups, respectively.
 
2) Multiple Imputation for Monotone Missing data Completing the imputation for non-monotone missing data, each ACR components (i.e. TJC-68, SJC-66, SGAP, SGA, PGA, HAQ-DI, CRP) at Week 12 will be imputed, respectively, based on the regression model with treatment group (Placebo, ASP015K 100 mg, ASP015K 150 mg, Etanercept) as factor and all values up to Week 12 as covariate. In this method, using seed as 12345, 1000 imputed datasets for each ACR components will be created based on SAS ver. 9.4 PROC MI procedure, monotone reg statement. Then, ACR20 response at Week 12 will be calculated with imputed datasets for each ACR components based on the same method described in Section 6.1.1.
 
<Step2>Analysis Part Based on 1000 Imputed datasets created at Step1, ACR20 at Week 12 in each treatment group will be summarized by Imputed datasets. Also, the difference in ACR20 at Week 12 between ASP015K 100 mg / 150 mg, Etanercept and placebo and their standard error will be calculated. Moreover, the log odds ratio to placebo in ACR20 at Week 12 and its standard error will be calculated by each Imputed datasets using logistic regression model with treatment group, the prior biologic-DMARD-IR (No, Yes), concomitant, DMARD use (No, Yes) and study region (Japan, Korea, and Taiwan) as factor.

Imputation Method		Explanation/Instruction
4	Multiple Imputation, assuming Missing at Random Mechanism	
<Step3>Combine Part
 
In accordance with Rubin's rule (Little and Rubin, 2002), the 1000 estimated ACR20 response rate in each treatment groups are combined. In addition, the difference between ASP015K 100 mg and placebo, the difference between ASP015K 150 mg and placebo, the difference between Etanercept and placebo, and 95% confidence interval for the difference will be combined. Moreover, the Wald's chi-squared test using logistic regression model with treatment group (Placebo, ASP015K 100 mg, ASP015K 150 mg), the prior biologic-DMARD-IR (No, Yes), concomitant, DMARD use (No, Yes) and study region (Japan, Korea, and Taiwan) as factor will also be calculated.

Imputation Method		Explanation/Instruction
5	Placebo Multiple Imputation (pMI)	
Placebo Multiple Imputation, assuming the statistical behavior of ASP015K 100 mg or 150 mg treated patients who discontinue becomes that of placebo-treated patients after the time of dropout will be conducted in the following procedure.
 
<Step1>Imputation Part
 
1) Multiple Imputation for Non-Monotone Missing data If non-monotone missing pattern exists, then those non-monotone missing data will be imputed by adapting Markov Chain Monte Carlo method, using each non-missing ACR components data up to Week 12. Imputation will be conducted by each ACR components (i.e. TJC-68, SJC-66, SGAP, SGA, PGA, HAQ-DI, CRP), and treatment groups, respectively.
 
2) Multiple Imputation for Monotone Missing data Completing the imputation for non-monotone missing data, each ACR components (i.e. TJC-68, SJC-66, SGAP, SGA, PGA, HAQ-DI, CRP) at Week 12 will be imputed, respectively, based on the regression model using only data from the placebo group up to Week 12. In this method, using seed as 12345, 1000 imputed datasets for each ACR components will be created based on SAS ver. 9.4 PROC MI procedure, monotone reg statement. Then, ACR20 response at Week 12 will be calculated with imputed datasets for each ACR components based on the same method described in Section 6.1.1.
 
<Step2>Analysis Part For 1000 Imputed datasets created at Step1, ACR20 at Week 12 in each treatment group will be calculated. Also, the difference in ACR20 at Week 12 between ASP015K 100 mg / 150 mg, Etanercept and placebo and their standard error will be calculated. Moreover, the log odds ratio to placebo in ACR20 at Week 12 and its standard error will be calculated by each Imputed datasets using logistic regression model with treatment group, the prior biologic-DMARD-IR (No, Yes), concomitant, DMARD use (No, Yes) and study region (Japan, Korea, and Taiwan) as factor.

Imputation Method		Explanation/Instruction
5	Placebo Multiple Imputation (pMI)	
<Step3>Combine Part
 
In accordance with Rubin’s rule (Little and Rubin, 2002), the 1000 estimated ACR20 response rate in each treatment groups are combined. In addition, the difference between ASP015K 100 mg and placebo, the difference between ASP015K 150 mg and placebo, the difference between Etanercept, and 95% confidence interval for the difference will be combined. Moreover, the Wald's chi-squared test using logistic regression model with treatment group (Placebo, ASP015K 100 mg, ASP015K 150 mg), the prior biologic-DMARD-IR (No, Yes), concomitant, DMARD use (No, Yes) and study region (Japan, Korea, and Taiwan) as factor will also be calculated.

For use in all DAS28 and DAS28-based analyses, unless otherwise specified in Section 10.2 Appendix 1
		
6	LOCF DAS28 CRP components	
 • LOCF all missing DAS28 CRP component value(s) and then calculate the DAS28 score.

Missing Data in HAQ-DI

For HAQ-DI, there are 20 items in 8 categories, with each category having 2 or 3 questions. A subject must have a score in ≥ 6 of the 8 categories, otherwise the HAQ-DI cannot be computed and will be considered missing for data summarization and analysis purposes. If responses to individual questions within a category are missing, they are not imputed. Therefore, the score in each category is based on non-missing responses. A category score is missing when all responses within a category are missing.

Missing Data in SF-36v2

For SF-36v2, there are 8 scales (domains). Missing values will be imputed if at least half of the items in the domain that included the missing item score(s) are non-missing. In that case, the missing value will be imputed with the average score of the non-missing item scores in this domain.

Missing Data in WPAI

For WPAI Scale Score, each score will be computed on condition that the all of the questions for each score will not be non-missing.

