6 ANALYSIS VARIABLES

6.1 Efficacy Endpoints

6.1.1 Primary Efficacy Endpoints

- ACR20 response rate at Week 12 or early termination (Week 12/ET)

Definitions

ACR20 response rate at Week 12 or early termination (Week 12/ET)

It is defined as percentage of subjects achieving ACR 20 response at Week 12/ET, based on C-reactive protein (CRP). ACR20 is a binary variable, with levels responder and non-responder.

Responder :

A subject will be defined as an ACR20-CRP responder at any time point (e.g. Week 12/ET) if the subject meet ALL the following American College of Rheumatology (ACR) response criteria:

- At least 20% reduction from baseline at the time point (e.g. Week 12/ET) in the number of 68 tender joint count (TJC-68)

AND

- At least 20% reduction from baseline at the time point (e.g. Week 12/ET) in the number of 66 swollen joint count (SJC-66)

AND

- At least 20% reduction from baseline at the time point (e.g. Week 12/ET) in ANY 3 or more of the 5 following ACR components
 - Subject's global assessment of arthritis pain (SGAP) (assessed using a 100 mm VAS ; score of 0 indicates no pain, and score of 100 indicates very severe pain)
 - Subject's global assessment of arthritis (SGA) (assessed using a 100 mm VAS; score of 0 indicates no disease activity, and score of 100 mm indicates very severe disease activity)
 - Physician's global assessment of arthritis (PGA) (assessed using a 100 mm VAS; score of 0 indicates no disease activity, and score of 100 mm indicates very severe disease activity)

- Health Assessment Questionnaire – Disease Index (HAQ-DI; score ranges from 0 to 3 with higher scores indicating greater disability)
- CRP (Higher values indicate greater inflammation)

Baseline is defined in Section 7.11.4. A negative percent change indicates a reduction from baseline (i.e., a favorable outcome). If the baseline value is 0 in some of ACR components, then that component is regarded as non-responder at that component and used for ACR calculation. The handling of missing data in ACR components is described at Section 7.11.2.

Non-responder: A subject will be defined as an ACR20-CRP non-responder at the time point (e.g. Week 12/ET), if the subject does not meet the ACR20-CRP responder criteria.

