7.11.4 Visit Windows

The acceptable time ranges of the efficacy and safety examinations, observations, etc. from the date of initial study treatment (Day 1) are defined as follows. If there are multiple data available over the same period of time, the data obtained on the date closest to the reference date will be utilized; the later date will be applied if the number of days from the reference date is equal. Subjects who have no evaluable post-dose data on ACR20, ACR50, and ACR70 response rates will be counted as non-responders and included in the analysis at the end of Week 12 (Week 12 or at early termination before Week 12).

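### The MI and pMI sensitivity analyses impute the seven ACR components separately, so imputed ACR20 in dropouts is biased

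*SAP*

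**What the plan says.** SAP 6.1.1 defines an ACR20 responder as a patient with at least 20% reduction in TJC-68, in SJC-66, and "in ANY 3 or more of the 5 following ACR components". It is a joint event within one patient at one visit.

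Method 4 (MI under missing at random) has two imputation steps. For non-monotone gaps it uses MCMC: "Imputation will be conducted by each ACR components (i.e. TJC-68, SJC-66, SGAP, SGA, PGA, HAQ-DI, CRP), and treatment groups, respectively". For dropouts the wording is "each ACR components (i.e. TJC-68, SJC-66, SGAP, SGA, PGA, HAQ-DI, CRP) at Week 12 will be imputed, respectively, based on the regression model with", and the predictors listed are the study arm as a factor and all values up to Week 12 as covariates. The output is described as follows: "using seed as 12345, 1000 imputed datasets for each ACR components will be created based on SAS ver. 9.4 PROC MI procedure". Only then is the endpoint formed: "ACR20 response at Week 12 will be calculated with imputed datasets for each ACR components".

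Method 5 (pMI) repeats the structure, with the monotone step "based on the regression model using only data from the placebo group up to Week 12".

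SAP 7.4.1.2 lists both methods among the checks on the robustness of the primary analysis, which itself uses LOCF (SAP 7.4.1.1).

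**The concern.** A patient who drops out before Week 12 usually has no Week 12 value for any component. If each component is drawn from its own model, the seven Week 12 values are linked only through the patient's history. The part of their correlation that arises at Week 12 itself is not estimated anywhere. Two outcomes are possible, and the SAP does not say which applies:

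- **Independent draws given history.** Components improve together too rarely, and dropouts' imputed ACR20 is too low.
- **Separate PROC MI calls that each restart at seed 12345 with the same missing pattern.** The random draws may be shared across components. Components then improve together too often, and imputed ACR20 is too high. This is possible, not certain.

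Reading the covariate list to include other components' earlier values does not help, because the same-visit residual correlation is still omitted.

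These are the only model-based missing-data checks on a LOCF primary analysis. Method 5 says that dropouts on active drug behave like placebo patients, whose components move together; separately drawn components do not. Method 4 would give a biased ACR20 even if data were missing at random.

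**Working it through.** **1. Planning rates.** SAP Section 4 assumes ACR20 of 25%, 54.5% and 65.5% and states that 62 per group give 90% power for 100 mg at two-sided 0.05. Check:

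- Uncorrected n = [1.960√(2×0.3975×0.6025) + 1.282√(0.25×0.75 + 0.545×0.455)]² / 0.295² = 55.7.
- Continuity-corrected n = (55.7/4) × [1 + √(1 + 4/(55.7×0.295))]² = 62.3, or 63 rounded up. Exact power at 62 is 90.4%.

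The stated figure is reproduced, so these rates anchor what follows.

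**2. How much correlation survives.** Let ρ be the true between-component correlation at Week 12, r an equal correlation between visits, and R² the share of Week 12 variance explained by a component's own history. R² = r² if Week 4 is the last visit, and 2r²/(1+r) if Week 8 is. For r = 0.5–0.7, R² runs from 0.25 to 0.98/1.7 = 0.576. For assumed ρ = 0.3–0.7, the correlation of imputed values is:

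- Independent draws: ρR², from 0.3×0.25 = 0.08 to 0.7×0.576 = 0.40.
- Shared draws: 1 − R²(1−ρ), from 1 − 0.576×0.7 = 0.60 to 1 − 0.25×0.3 = 0.925.

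Under this structure other components' earlier values add no information, so a wider covariate list gives the same result.

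**3. Effect on ACR20.** The simulation used 120,000 subjects per arm in 36 scenarios (ρ and r as above; SD 40 or 60 points; last visit Week 4 or 8; three dropout patterns). Arm means were solved to give the planning rates. The documents give no planned dropout rate, so missingness was taken as 17.9%, 10.9% and 6.9% (placebo, 100 mg, 150 mg), the AE discontinuation rates in the earlier Japanese trial (Protocol 1.3). Subjects with no post-baseline data were left out because the SAP makes them non-responders. Joint draws returned 24.5–25.8% for a true 25%. Shifts in the difference from placebo, in points, relative to the joint draw:

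| Who drops out | Draws | Placebo dropouts: imputed (correct) | MI shift | pMI shift |
|---|---|---|---|---|
| Unrelated to history | Independent | 11–21% (25%) | +0.4 to +2.1 | +0.3 to +1.6 |
| Unrelated to history | Shared | 29–41% (25%) | −2.2 to −0.3 | −1.8 to −0.3 |
| Worst 20–30% of histories | Independent | 0–5% (2–11%) | −1.0 to +0.9 | −0.3 to +0.7 |
| Worst 20–30% of histories | Shared | 4–26% (2–11%) | −1.8 to +0.3 | −1.8 to +0.1 |

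**4. From dropouts to the contrast.** Arm shift = missing fraction × shift among dropouts. Two cases from a second simulation grid (ρ 0.3–0.7, r 0.4–0.8, independent draws) show why the sign varies:

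- ρ = 0.7, r = 0.4, random dropout. Shifts among dropouts are −15.9, −12.9 and −9.1 points. Arm shifts are 0.179×(−15.9) = −2.85, 0.109×(−12.9) = −1.41 and 0.069×(−9.1) = −0.63. The differences move by +1.4 (100 mg) and +2.2 (150 mg).
- ρ = 0.7, r = 0.8, poor early responders drop out. Shifts among dropouts are −1.6, −10.0 and −11.2. Arm shifts are −0.29, −1.09 and −0.77. The differences move by −0.8 and −0.5.

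Over that grid the shift was −0.8 to +2.2 (independent) and −2.6 to +0.2 (shared). A third simulation with another visit-correlation structure gave about −1.0 to +2.5 and −3.1 to +0.2.

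**5. Scale.** The standard error at 100 per arm is √[(0.25×0.75 + 0.545×0.455)/100] = 6.6 points for 100 mg and √[(0.25×0.75 + 0.655×0.345)/100] = 6.4 for 150 mg. So 2.2/6.4 is about one third, and 3.1/6.4 about one half.

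**6. Does joint imputation repair it?** This run used 100 per arm, 20 imputations, 1500 trials, estimated imputation models, ρ = 0.5, r = 0.6, and mostly poor responders dropping out:

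| | Placebo | 100 mg | Difference |
|---|---|---|---|
| Full data | 24.9% | 54.3% | 29.4 |
| Joint MI | 25.0% | 54.3% | 29.2 |
| Separate, independent | 23.9% | 53.1% | 29.2 |
| Separate, seed restarted | 26.4% | 55.4% | 29.0 |

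Monte Carlo error of the arm biases is 0.03–0.04 points. Joint imputation removes the arm-level bias (1.0–1.5 points with separate imputation).

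**The case against.** PROC MI's monotone regression always fits one regression per variable, so the monotone sentence could describe a single run listing all seven components. Components already imputed at Week 12 would then predict the later ones, and the correlation would be kept. That reading does not fit the rest of the text: the MCMC step is explicitly by component, and 1000 datasets are made for each component. If the program is in fact joint, the wording still needs correcting.

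The remaining points largely stand:

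- In the finite-sample run, separate imputation moved the difference by only 0.0–0.2 points from joint MI, because the arm biases nearly cancel.
- The largest shift in the table needs both dropout unrelated to history and shared draws. Protocol 1.3 reports aggravated RA as the most common reason for AE discontinuation (21 of 32), which favours the poor-history rows.
- The missingness rates are a proxy. They come from a single-agent trial, include early discontinuers who may have no post-baseline data, and ignore other withdrawal reasons. An early-termination visit on Days 78–92 counts as Week 12. True missingness could be lower or higher.
- For method 4 the fault is a misspecified imputation model, not a breach of the missing-at-random mechanism.
- These are two of seven sensitivity analyses. Power for 100 mg at 100 per arm falls only from 99.2% to 98.3% if the difference shrinks by 2 points.

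**Conclusion.** The concern holds. As written, methods 4 and 5 do not model the Week 12 residual correlation between components. The imputed ACR20 of dropouts is therefore biased, downward with independent draws and upward with shared draws. Among dropouts the error can exceed 10 points. In the contrast with placebo it is at most 2.2 points in the main simulation and about 3 across all three, with no fixed direction. It would not overturn differences of 29.5 or 40.5 points. The LOCF primary analysis and the NRI, PPS and observed-data analyses are unaffected.

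The sizes rest on assumed correlations and SDs and on borrowed missingness rates. The main simulation treated imputation parameters as known, and SAS was not run. The structural fault does not depend on these assumptions. It should be corrected because the two analyses are meant to test the missing-data assumptions and the remedy is cheap.

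**What to change.** Rewrite methods 4 and 5 so that all seven components are imputed together:

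1. Use one dataset with component-by-visit columns.
2. Run one joint MCMC step for non-monotone gaps, and state its seed, which the SAP omits.
3. Run one monotone regression with one stated seed, visit by visit. The predictors are all components' earlier values and the components already imputed at the same visit. For pMI, fit this model on placebo data.
4. Produce 1000 datasets that each hold all seven components, then derive ACR20.

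It would also help to repeat within both methods the general rules that "if subject does not have any post-baseline values, then that subject will be defined as an ACR20-CRP non-responder" (7.11.2) and "Subjects who have no evaluable post-dose data on ACR20, ACR50, and ACR70 response rates will be counted as non-responders" (7.11.4). They already apply, so this is only for clarity.

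The cost is SAP wording and reprogramming of two sensitivity analyses, with no new data. One small downside is that seven components at baseline and Weeks 4, 8 and 12 make 7×4 = 28 variables for about 100 subjects per arm, so the MCMC step may need a ridge prior.

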10.7 Appendix 7: Computation of WPAI Scale Score

Work Productivity and Activity Impairment Questionnaire: WPAI

In this study, the following scoring methods are applied. These scoring methods are based on the specific health problem version of WPAI (WPAI:SHP).

Question Number	Contents
1.	1. Are you currently employed (working for pay)?
2.	2. During the past seven days, how many hours did you miss from work because of problems associated with your rheumatoid arthritis?
3.	3. During the past seven days, how many hours did you miss from work because of any other reason, such as vacation, holidays, time off to participate in this study?
4.	4. During the past seven days, how many hours did you actually work?
5.	5. During the past seven days, how much did your rheumatoid arthritis affect your productivity while you were working?
6.	6. During the past seven days, how much did your rheumatoid arthritis affect your ability to do your regular daily activities, other than work at a job?

Scores:

Multiply scores by 100 to express in percentages.

- Percent work time missed due to problem: $Q2/(Q2+Q4)$
- Percent impairment while working due to problem: $Q5/10$
- Percent overall work impairment due to problem:
 $Q2/(Q2+Q4)+[(1-(Q2/(Q2+Q4)))x(Q5/10)]$
- Percent activity impairment due to problem: $Q6/10$

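### The WPAI missing-data rule is worded backwards and, read as intended, sets overall work impairment to missing when Q5 is blank in a subject who missed all work because of RA, although the formula already gives 100%

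*SAP*

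**What the plan says.** SAP 7.11.2 has one sentence on missing WPAI data: "each score will be computed on condition that the all of the questions for each score will not be non-missing". It names no exception and no imputation. The same section gives explicit partial-data rules for HAQ-DI and SF-36v2.

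SAP Appendix 7 (10.7) lists six questions. Those that matter here are:

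- Q1: "Are you currently employed (working for pay"
- Q2: "how many hours did you miss from work because of problems associated with your rheumatoid arthritis"
- Q4: "During the past seven days, how many hours did you actually work"
- Q5: "how much did your rheumatoid arthritis affect your productivity while you were working"

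Four scores are built from the questions. Work time missed uses Q2 and Q4, impairment while working uses Q5, and activity impairment uses Q6. The fourth, "Percent overall work impairment due to problem", combines Q2, Q4 and Q5; its expression begins "Q2/(Q2+Q4)+[(1-(Q2/(Q2+Q4)))x(Q5/10" and then closes its brackets. For all four the instruction is "Multiply scores by 100 to express in percentages".

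Change in WPAI is a secondary efficacy variable in Protocol 2.3.2.1. SAP 7.4.2 and Table 19 (row 15.1) plan an ANCOVA against placebo at Weeks 4, 8, 12 and 12/ET. Footnote 3 of that table limits the ANCOVA to change; raw values are only described. Under SAP 7.1, a subject with a missing baseline value is left out of change from baseline at every visit.

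**The concern.** There are two faults in the one sentence.

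First, the double negative reverses the condition. Followed to the letter, it would compute scores only from unanswered questionnaires. The only workable reading is that every item a score uses must be answered.

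Second, that reading discards a value that is already known. Q5 has nothing to refer to when the subject worked zero hours, so a blank is the natural response. If Q2 is positive and Q4 is zero, the overall score does not depend on Q5, yet the rule makes it missing because Q5 is missing.

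Missingness of this kind depends on the outcome: it arises only at 100%, the worst value on the scale. At baseline it costs the subject every later change value for this score, including any return to work. At a later visit it hides a fall to zero hours. At Week 12/ET the SAP takes the value closest to Day 85 within Day 2 to Day 92 (7.11.5, Table 11), so an earlier and better score may stand in for it.

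**Working it through.** The documents give no sample size, power or expected value for WPAI, so there is no planned figure to reproduce. The check is to evaluate the Appendix 7 formula directly.

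**Formula.** Let A = Q2/(Q2+Q4). Overall work impairment = 100 × [A + (1 − A) × Q5/10].

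**No hours worked because of RA (Q2>0, Q4=0).** A = Q2/(Q2+0) = 1. The score is 100 × [1 + 0 × Q5/10] = 100 for any Q5.

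| Q2 | Q4 | A | Score at Q5=0 | Score at Q5=10 |
|---|---|---|---|---|
| 40 | 0 | 1.0 | 100 | 100 |
| 8 | 0 | 1.0 | 100 | 100 |
| 36 | 4 | 0.9 | 90 | 100 |
| 20 | 20 | 0.5 | 50 | 100 |
| 0 | 0 | 0/0 | undefined | undefined |

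The first two rows are flat over all eleven values of Q5. The next two are not, so an exception for a blank Q5 is justified only when Q4=0. The last row, for example a full week of vacation, which Q3 anticipates, shows that the exception must also require Q2>0.

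**Status of the four scores when Q1=yes, Q2>0, Q4=0 and Q5 is blank, under the intended rule.**

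- Work time missed: needs only Q2 and Q4; computed as 100%.
- Impairment while working: Q5 is blank, and the score is legitimately undefined.
- Activity impairment: needs only Q6; computed.
- Overall work impairment: set to missing, although Q2 and Q4 fix it at 100%.

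Since A + (1 − A) × Q5/10 is never below A, overall impairment cannot be lower than work time missed. The outputs would therefore show 100% for the smaller quantity and nothing for the larger.

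**Size, for one arm's mean level only.** Suppose a share f of employed subjects is at zero hours with Q5 blank, and the rest average m%. The mean with them is 100f + (1 − f)m and without them is m, so dropping them lowers the mean by f × (100 − m). The documents give neither f nor m; both are assumed:

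- f = 1%, m = 50%: 0.01 × 50 = 0.5 points
- f = 2%, m = 45%: 0.02 × 55 = 1.1 points
- f = 5%, m = 30%: 0.05 × 70 = 3.5 points
- f = 10%, m = 30%: 0.10 × 70 = 7.0 points

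**Direction, for the drug-placebo difference in change.** Losing an improvement on drug or a worsening on placebo shrinks the difference. Losing an improvement on placebo or a worsening on drug enlarges it. The documents do not say how these losses would divide between the arms.

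**The case against.** The strongest reply is that the case may rarely or never arise. The documents show no instruction to skip Q5 when no hours were worked, and neither the questionnaire nor its completion guide is included. A subject who fills in Q5 anyway is scored 100% by the existing formula. This stands: the point holds only if Q5 is left blank, and that a blank is likely is an inference from the item's wording.

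A reader might infer that such subjects drop out of the WPAI analysis altogether. They do not. Work time missed still records 100%, activity impairment is still computed, and impairment while working has no meaning for a week without work.

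A reader might also infer that the rule biases the comparison towards no difference, or that figures such as 1.1 to 3.5 points measure that bias. Neither is supported. Shrinkage requires lost improvements to lie mainly on drug and lost worsenings mainly on placebo. That is plausible if the drug works, but it does not follow from the rule. The point figures are shifts in one arm's mean level under assumed inputs, whereas the test is on change; similar shares in both arms would largely cancel.

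Appendix 7 bases its scoring on the specific-health-problem version of the instrument. Whether that version's own rules cover this case cannot be checked here. The SAP text contains no such rule.

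None of this defends the reversed sentence or the loss of a score that two answered items already determine.

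**Conclusion.** The point holds in a limited form. The reversed wording is certain. Under the evident meaning, a blank Q5 with Q2>0 and Q4=0 turns a fully determined 100% overall work impairment into a missing value, and at baseline it removes the subject from all change analyses of that score. The loss is informative because it happens only at the worst value.

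The effect on the between-arm difference has neither a size nor a sign that the documents can supply. The one-arm mean shift of 0.5 to 7.0 points rests wholly on assumed shares of 1% to 10% and assumed means of 30% to 50% among the remaining employed subjects.

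The consequence is minor. One of the four WPAI scores is affected, WPAI is one of many secondary variables without multiplicity control (Protocol 7.4.2, SAP 7.4.2), and ACR20 does not use it. The change is worth making because it is exact and nearly free.

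**What to change.** In SAP 7.11.2, replace the sentence with a rule that each WPAI score is computed only when all the items it needs have been answered, and repeat this in Appendix 7 with two additions:

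- When Q1=yes, Q2>0 and Q4=0, percent overall work impairment is 100% regardless of Q5. Work time missed needs no special rule, because its formula already returns 100%.
- When Q2=Q4=0, percent work time missed and percent overall work impairment are missing. The quotient has no value there, so this documents the outcome and keeps the first exception from being applied too widely.

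Impairment while working stays missing when Q5 is blank.

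The cost is two lines of SAP text and the matching derivation code, with no new data. The change belongs in the SAP before unblinding; after that, SAP Section 1 requires it to be justified in the study report.
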